1. STUDY TITLE

Neurally Targeted Interventions to Reduce Early Childhood Anxiety

3. STUDY RATIONALE

Deficits of effortful control (EC) have been posited to underlie early emerging anxiety such that improving EC may help to reduce anxiety symptoms. This study will test a play-based EC training intervention (Kidpower-Structured Games) against an active comparator (Child-led Play) in clinically anxious preschoolers to test the hypothesis that EC training will improve EC and thereby reduce anxiety.

4. SPECIFIC AIMS/HYPOTHESES

Aim 1: Confirm that Kidpower-Structured Games engages neural and behavioral markers of EC. We hypothesize that Kidpower-Structured Games will produce greater increases in neurophysiological and behavioral markers of EC than Kidpower-Child-Led Play (CLP, active comparator).

Aim2: Assess the relationship between pre- to post-Kidpower-Structured Games change in neurobehavioral markers of EC and change in clinically significant anxiety. We hypothesize that increases in neurophysiological and behavioral measures of EC will relate to reductions in clinically significant anxiety from pre-to-post Kidpower- Structured Games. Exploratory analyses will examine the moderating effects of baseline threat reactivity on the relation between pre- to post-treatment increase in EC and reduction in anxiety severity.

Aim 3: Explore dosing effects of Kidpower-Structured Games on behavioral EC targets and anxiety symptoms. We hypothesize that greater at-home practice of Kidpower-Structured Games exercises will relate to greater engagement of neural and behavioral markers of EC targets and greater reduction in anxiety symptoms. Dosage will be assessed by weekly parent report on child practice of EC exercises at home (frequency, duration).

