5. BACKGROUND AND SIGNIFICANCE

Preschool anxiety is prevalent, with 20% of children affected (Bufferd et al, 2012). Among these, a majority will continue to experience symptoms throughout adolescence and adulthood (Bittner et al, 2007). Early childhood anxiety also predisposes to a host of negative, long-term outcomes, including major depression and substance abuse (Bittner et al, 2007; Zimmerman et al, 2003), underscoring the importance of early intervention.

We will test a neuroscientifically-derived intervention targeting effortful control (EC) skills, low levels of which have been linked to greater emotional reactivity and clinical anxiety. Defined as the ability to effectively regulate behavior and emotion, EC reflects the activity of frontal brain systems and can be indexed by an event-related brain potential, the error-related negativity (ERN) and time frequency interchannel phase synchrony (ICPS) (Moran et al, 2015). The ERN is a neurophysiological response, localized to the dorsal anterior cingulate cortex, signaling the need for adaptive behavioral adjustments following errors (Gehring et al, 2018). The ICPS reflects the transmission of this error signal to the dorsolateral prefrontal cortex in order to implement the specified control (Cavanagh et al, 2009).

Findings from our labs and the work of others have shown that reduced ERN and ICPS relate to behavioral deficits in EC and enhanced threat reactivity (Lo et al, 2015) similar to that documented in clinically anxious children (Meyer, 2017). In response, our team developed a child-friendly group EC training, Camp Kidpower-Structured Games, designed to increase ERN, ICPS and related EC behaviors in the service of decreasing anxiety symptoms in preschoolers. Results of our pilot study indicate that this brief EC training approach engaged the intended EC neural and behavioral targets and reduced anxiety symptoms (Schroder et al, 2022). Building on this pilot work, the current project aims to replicate and extend these findings in a larger sample using a randomized controlled design.

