The Kidpower-Structured Games condition will be tested against an active comparator "Child-led Play" condition (Kidpower-CLP). Kidpower-Structured Games will involve executive function training games, shown to improve executive function skills in preschoolers (Diamond and Ling, 2016) and tested previously for the treatment of children with ADHD (Halperin et al, 2013). Kidpower-CLP will permit identification of specific effects of the EC training by controlling for confounds including: a) participation in a fun playgroup; b) interaction with new children during activities; c) separation from parents; and d) time spent with new adults. As detailed next, Kidpower-CLP is derived from evidence based treatment for early childhood psychopathology; in this study, it will include structured play activities (art activities, dramatic play, and story time), but not EC games. Both Kidpower-Structured Games and -CLP conditions will be delivered to small groups of clinically anxious preschoolers by study team members at the same staff to child ratio.

Child-led play has been shown to foster the development of cognitive, physical, social, and emotional well-being of children (Ginsburg et al, 2007). Moreover, play is important to healthy brain development (Shonkoff and Phillips, 2000; Frost, 1998; Tamis-Lemonda et al, 2004). When play is allowed to be child driven, children practice decision-making skills, move at their own pace, discover their own areas of interest. Additionally, child-led play promotes healthy parent-child attachment. The most widely employed early childhood psychotherapy, Parent Child Interaction Therapy (PCIT), focuses on Child-led Play for the first half of treatment. During this portion of PCIT, children experience child-directed play with their parents to encourage warm, secure caregiver-child relationships (Lieneman et al, 2017). The child-led play condition in Camp Kidpower gives children the opportunity to direct their own play at camp, while training parents to deliver child-led play at-home. As such, it fosters development across cognitive, social, neural and relational domains.

6. RESEARCH DESIGN AND METHODS (1 page maximum)

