Participants are randomized to a camp-style intervention ("Camp Kidpower"), which includes either EC training (Kidpower-Structured Games) or child-led playgroup (active comparator; Kidpower-CLP). Before and after the 4-week intervention, a multi-level assessment will be completed, including clinical interview with parent about their child's anxiety symptoms, parent-report surveys on child and self, lab-observed behavioral tasks and electroencephalogram (EEG) with child. Primary analyses will test for group mean differences in neurophysiological and behavioral indices of EC from time 1 (pre-intervention) to time 2 (post-intervention) among children assigned to Kidpower- Structured Games training compared to those assigned to Kidpower-CLP. Secondary analyses will test relationship of changes in neurophysiological targets with change in EC behaviors and change in anxiety severity.

The Kidpower-Structured Games were adapted from a group-based intervention originally designed to treat EC deficits in children with attention deficit hyperactivity disorder (Halperin et al, 2013) and a recently published review of executive function and effortful control interventions (Diamond and Ling, 2016). Kidpower-CLP was developed by the study team to include all of the same elements as Kidpower-Structured Games except for EC training games.

Both Kidpower-Structured Games and Kidpower-CLP will occur over 4-5 sessions, for approximately 3 hours each session. Sessions may be delivered back-to-back or over the course of four weeks. Times will be chosen to maximize child focus and energy and to provide the most convenience for families. Regardless of condition, children will begin with a group welcome activity, then will complete 1-2 of the intervention exercises for that day with their camp counselor. After a brief break and snack, children will complete the remaining 1-2 intervention exercises with their camp counselor, then come back together for a final group activity. The last 30 minutes of camp will include parents, who will be assigned daily homework involving the same play as at camp to complete with their child in between camp sessions. Two parent meetings (led by the lead camp counselor) will take place; the first will occur prior to the beginning of camp to orient parents, and the second will be held mid-way through camp to answer questions that may have arisen.

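### No listed analysis compares anxiety between the randomised arms, although the study's hypothesis is that EC training, tested against Child-led Play, reduces anxiety

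*Combined protocol and SAP*

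**What the plan says.** Section 3 (Study Rationale) says that Structured Games will be set against an active comparator, Child-led Play, "to test the hypothesis that EC training will improve EC and thereby reduce anxiety". Section 5 recalls a pilot that reduced anxiety symptoms and says "the current project aims to replicate and extend these findings in a larger sample using a randomized controlled design". On the role of the comparator it adds: "Kidpower-CLP will permit identification of specific effects of the EC training by controlling for confounds".

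The analyses are listed in two places.

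- Section 4, Aim 1, is a between-arm hypothesis on EC markers: "Kidpower-Structured Games will produce greater increases in neurophysiological and behavioral markers of EC than" Child-led Play. Aim 2 is to "Assess the relationship between pre- to post-Kidpower-Structured Games change in neurobehavioral markers of EC and change in clinically significant anxiety", with an exploratory moderation by baseline threat reactivity. Aim 3 relates home practice of Structured Games to EC and to anxiety.
- Section 6 says: "Primary analyses will test for group mean differences in neurophysiological and behavioral indices of EC", comparing the two arms. It continues: "Secondary analyses will test relationship of changes in neurophysiological targets with change in EC behaviors and change in anxiety severity". It does not say which arm or arms that secondary analysis uses.

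Section 6 also has the parent interviewed about the child's anxiety before and after the intervention, so the outcome exists in both arms.

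**The concern.** The hypothesis has two links, from training to EC and from training through EC to anxiety, and both are framed against Child-led Play. Only the first has a randomised comparison. The second rests on whether children whose EC rose more also had a larger fall in anxiety. Randomisation does not protect that relation. Maturation, engagement or any other process that varies between children can move both measures, in either arm.

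A positive Aim 1 with a positive Aim 2 would naturally be read as support for the whole hypothesis, yet neither asks whether anxiety fell more with EC training than with Child-led Play. The features the comparator is meant to control (a playgroup, new children, separation from parents, new adults) could themselves change anxiety. For anxiety, only a contrast by arm removes them.

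**Working it through.** **Step 1. Outcome and contrast of each listed analysis.**

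| Analysis | Outcome | Contrast |
|---|---|---|
| Aim 1 (section 4); primary analyses (section 6) | EC markers | Between arms |
| Aim 2 (section 4) | Anxiety change against EC change | Association, pre to post Structured Games |
| Aim 2 exploratory (section 4) | The same relation, by baseline threat reactivity | Association |
| Aim 3 (section 4) | EC and anxiety against home practice | Association |
| Secondary analyses (section 6) | Change in neural targets against change in EC behaviours and anxiety | Association, arms not stated |

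Between-arm analyses with an anxiety outcome: none. Pooling both arms in the section 6 secondary analysis would still give an association.

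**Step 2. Can Aims 1 and 2 both succeed with no arm difference in anxiety?** The text gives no alpha, SD, effect size, allocation ratio or dropout, so there is no stated figure to reproduce and these inputs are assumptions. From section 6, the largest pooled sample is 71 + 43 + 20 = 134, or 67 per arm at an assumed 1:1 ratio. EC change and anxiety change are taken as bivariate normal with SD 1 and the same correlation r in both arms. The arm effect shifts EC only. Children are independent and there is one EC marker. Aim 1 is a two-sample t test on EC change and Aim 2 a correlation within Structured Games, both two-sided 5% and counted only in the hypothesised direction. There were 20,000 simulated trials per setting.

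| Both aims positive | EC effect 0 | 0.3 SD | 0.5 SD |
|---|---|---|---|
| 67 per arm, r = -0.2 | 0.9% | 14.9% | 30.6% |
| 67 per arm, r = -0.3 | 1.8% | 28.2% | 57.6% |
| 67 per arm, r = -0.4 | 2.4% | 37.3% | 75.9% |
| 53 per arm (about 20% dropout), r = -0.3 | 1.5% | 19.8% | 42.7% |
| 67 per arm, r = -0.3, association pooled over arms | 2.4% | 37.8% | 76.2% |

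As a check at 67 per arm and r = -0.3, Aim 1 is positive in 2.5%, 40.3% and 81.9% of trials and Aim 2 in 70.5%. The products are 0.025 × 0.705 = 0.018, 0.403 × 0.705 = 0.284 and 0.819 × 0.705 = 0.577, which agree with the table.

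In the same trials the arm t test on anxiety change is significant in 5.0% and favours Structured Games in 2.3%. Among trials with both aims positive it favours Structured Games in 4.1% (EC effect 0.3 SD) and 2.8% (0.5 SD).

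**Step 3. Precision of the missing comparison.** With 80% power, two-sided 5% and 1:1 allocation, the detectable difference in SD units is (1.960 + 0.842) × √(4 × DE / N). The design effect DE allows for camp groups, because "conditions will be delivered to small groups of clinically anxious preschoolers". With an assumed 6 children per group and an ICC of 0.05, DE = 1 + (6 - 1) × 0.05 = 1.25. Baseline adjustment at an assumed pre-post correlation of 0.5 multiplies the result by √(1 - 0.25) = 0.866.

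| N | DE | Unadjusted | Baseline-adjusted |
|---|---|---|---|
| 134 | 1 | 0.48 | 0.42 |
| 134 | 1.25 | 0.54 | 0.47 |
| 107 (134 × 0.8) | 1 | 0.54 | 0.47 |
| 107 | 1.25 | 0.61 | 0.52 |

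**Step 4. Timing.** The two other sites contribute 71 + 43 = 114 of at most 134 children, and 114/134 = 85%.

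**The case against.** The strongest reply is about scope. Section 7 presents the study as a test of whether the mechanism is plausible, Aim 1 is target engagement, and the primary analyses match it. Efficacy on anxiety against an active comparator is not one of the three aims, and Aim 2 is already worded as a relationship. This stands as a reason to leave the primary analysis alone. It does not dispose of section 3, which makes the fall in anxiety part of the hypothesis tested against Child-led Play. Narrowing section 3 to target engagement would remove the inconsistency, but would give up an answer that the randomised data can provide.

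Second, this is a short form. Section 6 carries a one-page limit and the summary of measures is kept in a separate upload, so a comparison that is not listed may still be planned. That is right, and the point is limited to the text supplied.

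Third, the percentages rest on assumed inputs and are close to the product of two powers. That is also right. They illustrate the gap and do not forecast a result. With no EC effect the joint rate is only about 2%.

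Fourth, an arm comparison estimates the total effect on anxiety, not the path through EC, which would need an analysis of arm, EC and anxiety together. That is true. But a claim that training lowers anxiety through EC, relative to Child-led Play, still needs the arm contrast.

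Finally, the comparison would be imprecise and specified late. Both limits are real, and the fix has to disclose them.

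**Conclusion.** The point holds for the supplied text and should be fixed. Every listed between-arm analysis has an EC outcome, and anxiety enters only through associations, so the listed analyses cannot show whether EC training reduced anxiety more than Child-led Play. This conclusion comes from reading the listed analyses and does not depend on the simulation.

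How often the gap could mislead does depend on assumptions. Over correlations of -0.2 to -0.4 with 67 per arm, both aims succeed without any arm effect on anxiety in about 15% to 37% of trials at an EC effect of 0.3 SD, and 31% to 76% at 0.5 SD. The primary EC analysis is not affected.

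**What to change.** 1. Add, as the first secondary analysis, an as-randomised comparison of time 2 anxiety severity between arms. Use one named measure, adjust for time 1 severity and site, allow for camp group, and report a 95% CI. Date the addition and state whether any outcome data by arm had been seen, because most of the sample comes from the other two sites and Michigan State has finished enrolment.
2. Base any conclusion that EC training reduces anxiety relative to Child-led Play on that comparison, and report Aim 2 as an association. Section 12 describes both arms as active interventions, so a null difference should not be read as no effect. Report what the interval excludes.
3. Optionally, run Aim 2 in both arms with an arm-by-EC-change term.

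If a fuller analysis plan already lists the comparison, cite it here instead.

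The cost is plan wording and one extra model on the parent interview already done before and after the intervention, with no new visits or children. There are two downsides. The interval may be wide. The specification may also not be fully prospective, and that includes the choice of measure, since section 6 names no single anxiety instrument.

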Data collected in the current study will be collapsed together with data collected using the same study protocol at Michigan State (N = 71), New York State Psychiatric Institute (N = 43) to test study aims.

In the current study, up to 20 participants will be enrolled at the Columbia University Site. The Michigan State University site has completed enrollment and will assist in data analysis.

7. RESEARCH PARTICIPANTS (2-3 paragraph maximum)

Children with clinical anxiety symptoms aged 4-5.99 years old

This study will examine the mechanistic plausibility of EC training for childhood anxiety, promoting developmental trajectories towards positive mental health.

Inclusion criteria

1. Participants must be 4.0-5.99 years old at time of consent.
2. Has primary clinical diagnosis of separation anxiety disorder, social anxiety disorder, generalized anxiety disorder, panic disorder, obsessive-compulsive disorder, and/or specific phobia if symptoms present more days than not.
3. Written informed consent by a parent/legal guardian.
4. Fluent in English (note: participant may be bilingual, but must be able to speak and understand fluent English to participate in study.)

Exclusion criteria

1. History of head injury
2. History of serious neurological illness or current medical illness
3. History of major depressive disorder (MDD)
4. History of post-traumatic stress disorder (PTSD)
5. History of neurodevelopmental delay, autism spectrum disorder (ASD), or intellectual disability
6. Currently taking medications that affect the central nervous system (e.g., stimulants for ADHD, SSRIs for anxiety/depression, alpha agonists for ADHD or tics).
7. Currently receiving psychotherapy or other behavioral interventions
8. Primary clinical diagnosis is selective mutism.
9. History of recent physically aggressive behaviors that have caused harm to other children
10. Sibling of a child who has participated or is currently participating in this protocol

Parents of children with clinical anxiety symptoms

Inclusion criteria

1. Fluent in English (note: Participant may be bilingual, but must be able to speak and understand fluent English to participate in Questionnaire study)
2. Parent lives with child at least 50% of time
3. Has access to internet and webcam
4. Written informed consent for self and for their child

Exclusion criteria

1. Under 18 years of age
2. Not able to meet scheduling demands of the study

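### Aim 2 states the EC-change/anxiety-change association for Structured Games without a Child-led Play contrast, so factors that vary between children can produce it without any EC-training effect

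*Combined protocol and SAP*

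**What the plan says.** Section 3 gives the trial's purpose as a causal chain: "to test the hypothesis that EC training will improve EC and thereby reduce anxiety". Section 4 divides this into aims. Aim 1 compares the two arms on EC markers and names CLP as the comparator. Aim 2 is to "Assess the relationship between pre- to post-Kidpower-Structured Games change in neurobehavioral markers of EC and change in clinically significant anxiety", and its hypothesis is that "increases in neurophysiological and behavioral measures of EC will relate to reductions in clinically significant anxiety from pre-to-post Kidpower- Structured Games". Neither Aim 2 sentence mentions CLP.

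Section 5 explains the comparator: "Kidpower-CLP will permit identification of specific effects of the EC training by controlling for confounds including" playing in an enjoyable group, meeting unfamiliar children, being apart from parents and spending time with unfamiliar adults.

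Section 6 confines the primary between-arm comparison to EC indices. For the rest it says: "Secondary analyses will test relationship of changes in neurophysiological targets with change in EC behaviors and change in anxiety severity". It does not say which children enter, and it gives no arm term, interaction or mediation model. The text describes no between-arm test of anxiety. Section 6 has the same pre and post assessments in both arms.

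**The concern.** Aim 2 is the only stated analysis that links EC change to anxiety change, so it carries the second half of the section 3 claim. As worded, it is an uncontrolled association inside one arm. Some children improve faster than others through natural course, or gain more from repeated testing or from the camp setting. If those children both score better on EC and are rated less anxious, the two changes correlate even though the EC games contributed nothing. CLP children go through the same testing and a camp that differs only in lacking the EC games. They would show whether the association also occurs without the games, but Aim 2 does not call on them.

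What is at stake is interpretation. A significant Aim 2 result is likely to be read as EC training lowering anxiety by way of EC, when the same slope might be present in CLP.

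**Working it through.** The documents give no alpha, power, correlation, allocation ratio or sample-size calculation, so there is no figure of the plan's own to reproduce. What follows is illustration.

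**Inputs.** Section 6 pools 71 children from Michigan State, 43 from New York State Psychiatric Institute and up to 20 at Columbia: 71 + 43 + 20 = 134 at most. Assumptions: 1:1 allocation, giving 67 per arm, with 50 per arm as a lower value; two-sided alpha of 0.05; one EC marker; a shared child-level factor giving a change-change correlation of size r = 0.2 to 0.3 in both arms.

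**1. Within-arm test when training has no effect.** Probability of significance ≈ Φ(atanh(r)·√(n − 3) − 1.96), with atanh(0.2) = 0.2027 and atanh(0.3) = 0.3095.

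| n in arm | r = 0.2 | r = 0.3 |
|---|---|---|
| 67 (√64 = 8.000) | Φ(1.622 − 1.96) = 0.37 | Φ(2.476 − 1.96) = 0.70 |
| 50 (√47 = 6.856) | Φ(1.390 − 1.96) = 0.28 | Φ(2.122 − 1.96) = 0.56 |

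Simulation of a shared factor explaining 20% or 30% of the variance of each change gave 37.5% and 70.5% at 67 per arm, and 29.1% and 57.5% at 50. With a share of zero but the same mean improvement in every child, the rate in the hypothesized direction was 2.3% to 2.5%, which is nominal. A common shift therefore creates no association. The factor must vary between children and act on both changes.

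**2. What Aim 1 adds.** With normal data and no training effect, the arm difference in mean EC change is independent of the within-arm correlation. At 67 per arm, both tests are significant in about 0.05 × 0.37 = 1.8% to 0.05 × 0.70 = 3.5% of trials. Simulation gave 2.0% to 3.4%.

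**3. Where Aim 1 does not help.** Suppose training raises EC by 0.5 SD (assumed), EC has no effect on anxiety, and the shared factor is as above. Aim 1 power at 67 per arm is 0.82. Aims 1 and 2 are then both significant in about 0.82 × 0.37 = 30% to 0.82 × 0.70 = 57% of trials.

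**4. Two candidate rules for crediting EC training.**

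- *Product rule (arm effect on EC, and EC-anxiety slope adjusted for arm, both significant).* In the scenario of step 3, the slope uses all 134 children: Φ(0.2027 × √131 − 1.96) = 0.64 and Φ(0.3095 × √131 − 1.96) = 0.94. The rule is met in about 0.82 × 0.64 = 53% to 0.82 × 0.94 = 77% of trials, although EC does nothing to anxiety.
- *Interaction rule (steeper slope in Structured Games).* When training raises EC by 0.5 SD and EC truly lowers anxiety with the same slope (0.3) in both arms, the interaction is significant in about 5% of trials, no more than under no effect. Even with true correlations of 0.3 and 0, its power at 67 per arm is Φ(0.3095/√(2/64) − 1.96) = Φ(1.751 − 1.96) = 0.42 (0.43 by simulation), against 0.70 for the within-arm test.

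**The case against.** The strongest reply is that Aim 2 promises only a relationship. If the correlation really is 0.2 to 0.3, finding it significant is a correct answer to that question. The mechanism claim needs Aim 1 as well, and Aim 1 is randomized. Both points stand. A reader might infer that the trial has a 37% to 70% chance of a false mechanism claim. It does not: that rate belongs to Aim 2 taken alone, and with no training effect the joint rate is about 2% to 3%. This protection covers only the step from arm to EC, as step 3 of the working shows.

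A reader might also infer that the plan restricts Aim 2 to Structured Games beyond doubt. That is the plain reading of section 4. However, section 6 names no arm, the exploratory moderation sentence in Aim 2 refers to treatment without naming one, and the pooled data are said to serve the study aims. A pooled analysis is not ruled out. Pooling without an arm comparison would still carry the shared factor, so this argues for aligning the two sections and does not remove the point.

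A third tempting inference is that regression to the mean, natural course or practice alone would create the association. A shift equal for all children does not.

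Finally, a similar slope in CLP would not refute the mechanism. Section 5 credits child-led play with cognitive and neural benefits of its own, so EC could rise and act on anxiety in both arms.

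**Conclusion.** The point holds as a gap in specification and interpretation. Aim 2 as worded has no CLP contrast, section 6 supplies none, and the association alone cannot support the causal claim in section 3. Under an assumed shared correlation of 0.2 to 0.3, the within-arm test is significant in about 37% to 70% of trials at 67 per arm and 28% to 56% at 50 per arm when training does nothing. These figures rest on 1:1 allocation, complete data and correlations that the documents do not give.

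The documents do not support saying that the trial's whole inference is uncontrolled, or that a within-arm correlation is invalid as description. Nor does using CLP make the EC-to-anxiety step causal: adjusting for arm leaves child-level confounding in place. The change should be made, but Aim 2 is secondary and the primary between-arm comparison of EC is unaffected.

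**What to change.** Align sections 4 and 6 so that Aim 2 is fitted in all randomized children: time-2 anxiety regressed on time-1 anxiety, EC change and arm. Report the EC-change slope with its confidence interval in each arm, and give the arm-by-EC-change interaction as a descriptive check. Report the randomized between-arm difference in anxiety beside it. Use the same model for the exploratory threat-reactivity moderation.

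Use neither the interaction nor the product of arm effect and slope as the criterion for crediting EC training, for the reasons in step 4 of the working. State in the plan that the EC-to-anxiety path is not randomized, and that a similar slope in both arms will be described as an association not specific to EC training.

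The cost is wording and slightly more analysis; no new data are needed. The interaction will have low power (about 43% for correlations of 0.3 and 0 at 67 per arm), and the mechanism conclusion will be more guarded.
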